8.6. End of Study Phone Visit (Day 31 \pm 7 Days)

The purpose of the Day 31 End of Study Phone Visit is to complete participant follow-up. This visit will be brief, and participants will be asked to report any new AEs and to answer questions regarding the status of their AD and concomitant medication use. Female participants of child-bearing potential will be asked whether they have tested positive to a pregnancy test since their last visit. Participants will be asked whether their partner has tested positive to a pregnancy test since their last visit, as applicable.

Any participant with an ongoing AE/Serious Adverse Event (SAE) at the time of this visit will continue to be followed until the event is resolved with or without sequelae or the AE/SAE stabilizes.

8.7. Unscheduled Visits

If disease activity increases, participants experience signs and symptoms as described on the study handcard, or other concerns arise between regularly scheduled visits, participants will be instructed to contact study personnel and may be asked to return to the study site for an “unscheduled” visit.

The following procedures, assessments, and laboratory measures will be conducted at the Unscheduled Visit:

- Assessment of AEs
- Physical examination, including assessment of AD severity (L-EASI, SCORAD, and local Pruritus NRS) by study physician or other qualified medical professional
- Pregnancy status of participant and partner of participant, as applicable
- Vital Signs
- Skin Swab collection, per investigator discretion
- Blood collection, per investigator discretion

If a participant presents to the research clinic with a suspected skin or systemic infection, skin swabs and/or blood samples may be collected. If collected, skin swab samples will be cultured and speciated to determine whether the transplant Staph strain caused the infection. A complete blood count with differential and blood culture will be performed on the blood sample, if collected, to assess for infection.

Participants will be given a handcard to present to clinical staff should they seek care for an infection at another facility. The handcard, as described in [Section 8.4](#), will state that the participant is currently in a clinical trial involving the application of non-pathogenic bacteria to the skin, list the sensitivities of *S. hominis*, and include instructions to call the research site if an infection of the skin or blood is suspected.

8.8. Visit Windows

Study visits should take place within the time limits specified above: the designated visit windows (*i.e. +/- n days*) for each scheduled visit are also indicated in [Appendix B Schedule of Events](#).

9. Mechanistic Assays

This section describes the proposed methodologies for this study. The techniques are state-of-the-art at the time of the writing of this protocol. Even so, the techniques will be updated and/or changed should there be additional technical breakthroughs in this area of research. Details of the laboratory processes are described in Standard Operating Procedures (SOPs) maintained by each laboratory.

9.1. Skin Swab Collection Procedure

Lesional and non-lesional swabbing areas (21 cm² total for each; 7 areas of 3 cm x 1 cm of lesional and non-lesional skin each) will be defined on each ventral arm at the Pre-treatment Visit. The lesional swab locations will be selected from the most severe lesional areas and may not be contiguous. Lesions closer to the antecubital region will take precedence in defining these areas. The non-lesional swab locations will be defined as areas of normal skin on the ventral arms and also may not be contiguous. In addition, a non-lesional swabbing area of 3 cm x 1 cm will be defined on the face at the Treatment Visit. The designated lesional and non-lesional sites for swabbing will be marked with a pen and nonidentifying digital photographs will be taken for reference during future visits. The number and location of swabs to be collected at each visit and time point are delineated in [Section 8](#) and the Schedule of Events. Each swab will cover a 3 cm² area. The lateral edge of the swab will be rubbed across the measured area in a cross-wise manner while rotating

the swab handle between the thumb and forefinger. Swabbing will be performed for at least 30 seconds. Refer to the MOP for additional details regarding the collection of skin swabs.

9.2. CFU Quantification of Live *Staphylococcus aureus* and CoNS

Skin swabs will be collected from pre-measured areas of lesional and non-lesional skin per [Section 9.1](#) using swabs premoistened with TSB. Collected swab tips for CFU quantification will be stored in 1 mL of 85% TSB/15% Glycerol and stored at -80°C until analysis. Live CoNS will be measured by counting CFU on mannitol salt agar with egg yolk, which is a selective media for staphylococcus species. CoNS and *S. aureus* can be distinguished by the colony morphology (CoNS: pink color without egg yolk reaction; *S. aureus*: yellow color with egg yolk reaction). Live *S. aureus* will be measured on Bear-Parker agar, which is a selective media for *S. aureus*. CFU quantification will give us quantification of live *S. aureus* and CoNS, as each will be grown in selective media and are important for our Primary Endpoint, Secondary Endpoint 1, and Exploratory Endpoints 2-5.

9.3. Quantification of *S. hominis* A9 CFU

To specifically identify colonies of *S. hominis* A9, 24-48 CoNS colonies will be picked from each culture plate and subjected to colony PCR using strain specific primers for the lantibiotic gene. CFUs of *S. hominis* A9 will be estimated from total CoNS CFU \times % of *S. hominis* A9 positive colonies. Quantification of *S. hominis* A9 estimated CFU will allow us to quantify *S. hominis* A9 specifically as outlined in Exploratory Endpoint 1.

9.4. Quantification of Bacterial DNA

Skin swabs will be collected from pre-measured areas of lesional and non-lesional skin per [Section 9.1](#), using swabs premoistened with Tris-EDTA buffer containing 0.1% TritonX-100 and 0.05% Tween-20 (w/v). Microbial DNA will be extracted with the PureLink Microbiome DNA Purification kit (Invitrogen). Abundance of DNA from total staphylococcus (G-staph), *S. aureus*, *S. hominis* and Sh-lantibiotic will be quantified by qPCR using genus-, species- and gene- specific primer sets, respectively. Quantification of bacterial DNA will allow for the assessment of specific shifts in the microbiome pre and post application of *S. hominis* A9, correlation between *S. hominis* A9 and Sh-lantibiotic, and correlation between *S. aureus* and Sh-lantibiotic, supporting the primary objective to assess the factors that overall influence survival.

9.5 Analysis of Antibiotic Sensitivity

Lesional skin swabs from the Baseline Visit and last Follow-Up Visit will be tested for antimicrobial sensitivity to erythromycin, tetracycline, and penicillin G. The same volume of bacterial swab samples from lesional skin at Baseline and last Follow-Up Visit time points will be spread on culture plates containing Mannitol-salt agar, a staphylococcus selective agar, without or with erythromycin (4 µg/mL), or tetracycline (8 µg/mL), or penicillin G (1 µg/mL). The concentration of each antibiotic was determined based on the minimal inhibitory concentration used to define ShA9 as resistant to these antibiotics. The proportion of CoNS with antibiotic sensitivity will be determined by comparing the CFU measured on duplicate agar plates without antibiotic to the CFU measured on agar plates with each antibiotic by the equation $[(\text{CFU without antibiotic containing plate} - \text{CFU with antibiotic containing plate}) / \text{CFU without antibiotic containing plate}]$. The proportion of antibiotic-sensitive CoNS detected at baseline will be compared to the proportion from swabs collected at the last Follow-Up Visit. If an increase in the proportion of antibiotic resistant CoNS is measured to be greater than 10%, resistant colonies will be evaluated to determine if they are ShA9. If these colonies are not ShA9, DNA sequencing will be performed to determine if they contain antibiotic resistance genes that were originally present in ShA9, thus indicating the likelihood for horizontal gene transfer.

10. Biospecimen Storage

Lesional and non-lesional skin swabs will be obtained from all study participants. These skin swabs and any derivative samples will be obtained for potential future analysis of additional parameters that describe the composition and function of the skin microbiome. Participants will be asked to give permission for long-term storage and future use during the consent process. All samples stored for future use will be kept in a central repository at UCSD.

Instructions for sample preparation, handling, storage, and shipping are included in the MOP. The PIs will be responsible for acknowledging and implementing all the regulations for classification, sample handling, packaging and labeling, permits or authorizations, and personnel training for shipment of biological and hazardous materials required for the conduct of this study.

11. Criteria for Participant and Study Completion and Premature Study Termination

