The skin pathogen *Staphylococcus aureus* has been reported to have highly efficient mechanisms for horizontal gene transfer between strains (Chen, et al., 2018; Humphrey, et al., 2021). Similar mechanisms of transfer have not been reported for *Staphylococcus hominis*. Additionally, in our analysis of ShA9, there has been no evidence of *S. aureus* lateral gene transduction elements in ShA9 and no evidence ShA9 has acquired virulence or antibiotic resistance genes via conjugative transposon from other species. Plasmids for antibiotic resistance genes or virulence factors also have not been found in our analysis of *S. hominis*. However, we did identify the presence of two prophages containing a betalactamase homolog in the ShA9 DNA sequence (unpublished data, [name] lab-UCSD). The antibiotic resistance profile present in ShA9 to beta-lactam antibiotics, tetracycline, and erythromycin is also already ubiquitously present in the healthy human skin microbiome (Oh, et al., 2014; Oh, et al., 2016; and Baron, et al., 2018); therefore, the effect of this occurrence is unclear. Due to the theoretical possibility of transfer of antibiotic resistance from ShA9 to *Staphylococci* present on the skin of study participants, we will investigate the antibiotic sensitivity to penicillin G, tetracycline, and erythromycin in CoNS isolated from skin swabs at baseline and at the last swab collection from lesional skin.

[figure not shown]

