7.4. Rescue Medications

If infection occurs, treatment will include topical and/or oral antibiotics depending on the severity of the infection clinically, and Cetaphil® lotion (for irritation and dryness). The antibiotic sensitivity profile of *Staphylococcus hominis* A9, includes sensitivity to ampicillin-sulbactam, cefazolin, cefoxitin, clindamycin, daptomycin, levofloxacin, linezolid, minocycline, moxifloxacin, mupirocin, nitrofurantoin, oxacillin, rifampin, trimethoprim-sulfamethoxazole, and vancomycin; intermediate sensitivity to doxycycline; and resistance to erythromycin, penicillin G and tetracycline. The antibiotic of choice will depend on the individual participant's medical history, including any possible contraindications to certain medications due to allergies or other concomitant medication use, but mupirocin will be the first line topical antibiotic of choice, and minocycline will be the first line oral antibiotic, followed by first generation cephalosporins, trimethoprim-sulfamethoxazole or rifampin. Contact allergic reactions to Cetaphil lotion or glycerol will be treated with mid-potency topical steroids, such as fluocinonide ointment 0.05%.

8. Study Procedures

A summary of complete study procedures is included in Appendix B Schedule of Events. To ensure participant safety, participants will be asked to comply with UCSD's current institutional policies and procedures related to COVID-19, which are based on recommendations from the Centers for Disease Control and Prevention when scheduling and attending their appointments.

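### Protocol 9.5 reads likely gene transfer from ShA9 without checking whether the resistance gene or strain was already on the participant's skin at Day 0

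*Protocol*

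**What the plan says.** Protocol 9.5 plates lesional swabs from baseline and from the last follow-up visit on agar without antibiotic and with each of erythromycin, tetracycline and penicillin G. Two things follow.

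- A comparison: "The proportion of antibiotic-sensitive CoNS detected at baseline will be compared to the proportion from swabs collected at the last Follow-Up Visit".
- A conditional laboratory step: "If an increase in the proportion of antibiotic resistant CoNS is measured to be greater than 10%, resistant colonies will be evaluated" to see whether they are ShA9. Those that are not ShA9 are sequenced to see "if they contain antibiotic resistance genes that were originally present in ShA9, thus indicating the likelihood for horizontal gene transfer".

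Protocol 7.4 lists ShA9's "resistance to erythromycin, penicillin G and tetracycline", the three drugs tested. On background, protocol 1.3 states: "The antibiotic resistance profile present in ShA9 to beta-lactam antibiotics, tetracycline, and erythromycin is also already ubiquitously present in the healthy human skin microbiome", and adds "therefore, the effect of this occurrence is unclear". The same section reports a possible mobile carrier: "we did identify the presence of two prophages containing a betalactamase homolog in the ShA9 DNA sequence". It calls transfer to skin staphylococci a theoretical possibility and gives that as the reason for the testing.

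SAP 7.2 repeats the formula for the sensitive proportion, and SAP 7.5.2 models its before-after difference. Neither contains the 10% threshold or the transfer step. Nowhere do the documents call for sequencing of baseline resistant colonies, state how closely a gene must match the one in ShA9, or use the placebo arm as a reference for this step.

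**The concern.** The last step of 9.5 has one input: whether a gene that ShA9 also has is present in a non-ShA9 colony collected after treatment. Presence after treatment is evidence of transfer only if the gene was not there before. The colonies examined have been selected for growing on the antibiotic, so each has some resistance mechanism, and the protocol itself says that this kind of resistance is common on skin.

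This is the only step in either document that draws a conclusion about transfer from a live product to resident staphylococci. A positive result would be read as bearing on the safety of ShA9 before the Phase 2 trial that section 1.2 anticipates. As written, the rule does not separate that result from resistance the participant already carried.

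**Working it through.** The documents give no error rate for this rule, so there is no figure to reproduce. The first step is a reading of the text. The others use assumed inputs.

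**1. Can the rule be met with no transfer?** Take a native CoNS strain, resistant at Day 0, carrying a gene that ShA9 also has. Suppose its share of CoNS rises enough for the resistant proportion to increase by more than 10%. Its colonies grow on the antibiotic plate, are not ShA9, are sequenced, and contain the gene. Every condition in 9.5 is met and nothing has been transferred.

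**2. Does the 10% threshold prevent this?** It decides when sequencing is done, not where a gene came from. Besides a shift in native flora, two things can pass it. The threshold is read here as 10 percentage points in one participant for one drug; 9.5 does not say whether it is absolute or relative, individual or pooled.

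- *Plate-count noise.* Assume independent Poisson counts, no ShA9, no transfer, and a true resistant share p of 0.3 to 0.8. By simulation the threshold is passed in 27–34% of comparisons at a mean of 30 colonies on the drug-free plate, 13–27% at 100, and 2.5–15% at 300.
- *Residual ShA9.* If ShA9 makes up a share s of CoNS, the resistant share rises by s(1 − p), so the threshold needs s > 0.10/(1 − p). That is 14%, 20% and 50% for p = 0.3, 0.5 and 0.8. A participant may leave follow-up once CoNS is below baseline + 100 CFU/cm². If native CoNS stays at its baseline B and ShA9 fills that allowance, s = 100/(B + 100). The threshold can then be passed when B is below 100/s − 100, about 600, 400 or 100 CFU/cm².

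In either case the native resistant colonies on the plate can then be sequenced.

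**3. How often would the last step be met with no transfer?** Let q be the share of native resistant colonies carrying a gene that ShA9 also has, and k the number sequenced. Both are assumed. With independent colonies, P(at least one) = 1 − (1 − q)^k.

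| q | k | P |
|---|---|---|
| 0.05 | 5 | 23% |
| 0.2 | 5 | 1 − 0.8⁵ = 67% |
| 0.2 | 10 | 89% |
| 0.5 | 5 | 97% |

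If a participant's resistant colonies are one clone, k does not matter and the probability is q: 20% at q = 0.2.

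**4. What would a Day 0 check achieve?** A strain forming a share r of Day 0 resistant colonies is missed by m colonies with probability (1 − r)^m.

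| r | m = 3 | m = 5 | m = 24 |
|---|---|---|---|
| 0.05 | 86% | 77% | 29% |
| 0.2 | 51% | 33% | 0.5% |

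A handful of colonies is too few. With 24, and a share of 0.2 at both times, the 67% falls to 0.672 × 0.8²⁴ = 0.3%. If the share was 0.05 at Day 0 and grew to 0.2, it falls only to 0.672 × 0.95²⁴ = 0.672 × 0.292 = 20%, before any requirement on sequence match.

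**The case against.** The strongest reply has four parts.

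- *The wording is cautious and may be stricter than it looks.* The text speaks of likelihood, not proof. Colonies are sequenced, and genes from ShA9 could mean a match to ShA9's own sequence. Section 9 leaves laboratory detail to SOPs, which may hold a matching criterion. This stands as a caveat. If such a criterion exists, 9.5 should cite it. It would still not address presence at Day 0 unless it says so.
- *Ubiquitous describes a resistance profile on healthy skin.* It does not say that identical genes are common on lesional atopic skin. This stands, and it is why no false-signal rate can be given.
- *The consequence is limited.* Endpoint 9 is the comparison of proportions. The sequencing is a conditional step in a pilot, and no stopping rule in 11.5 uses it. A sensitive flag for a theoretical risk is defensible. This stands as to weight, but a flag that will be examined further should not already be labelled as indicating transfer.
- *A stricter rule could hide a real transfer.* A gene that inserts in a new place would lack ShA9's flanking sequence. This stands and shapes the fix.

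A reader might also infer that the trial is almost certain to report at least one false transfer signal. The documents do not support that. It would need the 10% threshold applied to each participant and drug, which 9.5 does not say, plus values for q and k that appear nowhere. Nor do they support the inference that a true transfer could never be recognised: sequences would be in hand, and section 10 provides for stored samples from participants who permit it.

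**Conclusion.** The point holds as a fault in the inference. Following 9.5 as written can label pre-existing native resistance as likely transfer from ShA9, because nothing requires the gene or strain to have been absent at Day 0. This conclusion rests on the text alone and does not depend on the assumed numbers.

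The frequency is unknown. The 67% and 20% figures illustrate one assumed share (0.2) with 5 colonies, under independence and under a single clone; they are not estimates for this trial. Nor should a Day 0 check be expected to remove false signals altogether, since a strain that was rare at Day 0 can be missed even with 24 colonies. The matter is worth correcting because this is the only step that names transfer, but it is confined to an exploratory, conditional laboratory follow-up.

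**What to change.** **Keep the material.** Retain resistant colonies from the Day 0 pre-application antibiotic plates, or enough frozen swab stock to re-plate. Section 9.2 already freezes CFU swabs in glycerol medium at −80°C, and 9.5 already plates the baseline lesional swabs on the same antibiotics.

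**Test a stated number, in triggered participants only.** For example, 24 Day 0 resistant colonies, the lower number that 9.3 already picks per plate, tested for the gene and strain found after treatment. Report the number tested.

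**Replace the last sentence of 9.5 with a graded reading:**

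- *Pre-existing*: the same gene in the same strain is found among the Day 0 colonies.
- *Transfer likely*: the gene is not found at Day 0 and its sequence matches the ShA9 allele. Matching flanking or prophage sequence counts as supporting evidence but is not required.
- *Indeterminate, transfer not excluded*: anything else, including the gene found at Day 0 only in a different strain.

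Add the same reading to SAP 7.5.2. If a laboratory SOP already sets a matching criterion, cite it in 9.5.

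**Cost.** A short text change in each document and a little more laboratory work in triggered cases. No extra visits or swabs. Some results will be reported as indeterminate. The decision has to be made before Day 0 plates or stock are discarded, because the comparison may not be recoverable afterwards.

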11.1. Participant Completion

Participant participation will be defined as complete at the conclusion of the Day 31 End of Study Phone Visit.

11.2. Participant Stopping Rules and Withdrawal Criteria

Participants may be prematurely terminated from the study for the following reasons:

1. The participant elects to withdraw consent from all future study activities, including follow-up.
2. The participant is “lost to follow-up” (i.e., no further follow-up is possible because attempts to reestablish contact with the participant have failed).
3. The participant dies.
4. The Investigator no longer believes participation is in the best interest of the participant.
5. Individual safety stopping rules
 - a. Evidence of infection either cutaneously or systemically which in the opinion of the investigator makes the participant a poor candidate for receipt of the investigational product or requires treatment with a prohibited medication/therapy that would interfere with assessment of the study endpoints.
 - b. Severe worsening of AD which in the opinion of the investigator makes the participant a poor candidate for receipt of the investigational product or requires treatment with a prohibited medication/therapy that would interfere with assessment of the study endpoints.
 - c. Pregnancy in a female participant prior to the Treatment Visit (Refer to [Section 12.6](#)).

11.3. Participant Replacement

If any participants withdraw or are withdrawn prior to achieving CoNS elimination (CoNS CFU below baseline density measured before application of ShA9 + 100 CFU/cm²), additional participants may be enrolled as necessary to obtain a modified ITT sample as defined in [Section 13.4.1](#).

11.4. Follow-up after Early Study Withdrawal

If a participant is withdrawn from the study for any reason, the participant will be asked to complete a final visit by phone to assess any AEs since his/her last visit and to answer questions about the status of his/her AD. Any participant with an ongoing AE/SAE at the time of this phone contact will continue to be followed until the event is resolved with or without sequelae or until the AE stabilizes or until 30 days after the participant prematurely withdraws (without withdrawing consent)/or is withdrawn from the study, whichever occurs first.

11.5. Study Stopping Rules

Screening, enrollment, and application of treatment for this trial will be suspended pending immediate DSMB review for the following reasons:

- A single participant experiences any SAE for which there is a reasonable possibility that the investigational product caused the SAE
- The development of any severe (Grade 3) AE for which attribution is defined as related or possibly related

Follow up visits will continue to be conducted per protocol while under DSMB review. After review of the data, the DSMB will make recommendations regarding study conduct and/or continuation.

12. Safety Monitoring and Reporting

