12.2.3 Serious Adverse Event (SAE) or Serious Suspected Adverse Reaction

An adverse event or suspected adverse reaction is considered "serious" if, in the view of either the investigator or the Sponsor, it results in any of the following outcomes: Death, a life-threatening adverse event, inpatient hospitalization or prolongation of existing hospitalization, a persistent or significant incapacity or substantial disruption of the ability to conduct normal life functions, or a congenital anomaly/birth defect. Important medical events that may not result in death, be life-threatening, or require hospitalization may be considered serious when, based upon appropriate medical judgment, they may jeopardize the patient or subject and may require medical or surgical intervention to prevent one of the outcomes listed in this definition. Examples of such medical events include allergic bronchospasm requiring intensive treatment in an emergency room or at home, blood dyscrasias or convulsions that do not result in inpatient hospitalization, or the development of drug dependency or drug abuse (21 CFR 312.32(a)).

Elective hospitalizations are not to be reported as an SAE unless hospitalization is prolonged due to complications.

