12.3 Grading and Attribution of Adverse Events

12.3.1 Grading Criteria

The study site will grade the severity of AEs experienced by the study participants according to the criteria set forth in the NCI-CTCAE Version 5.0. This document (referred to herein as the NCI-CTCAE manual) provides a common language to describe levels of severity, to analyze and interpret data, and to articulate the clinical significance of all AEs. The NCI-CTCAE has been reviewed by the study investigators and sponsor and has been deemed appropriate for the participant population to be studied in this protocol.

AEs will be graded on a scale from 1 to 5 according to the following standards in the NCI-CTCAE manual:

Grade 1 = mild AE

Grade 2 = moderate AE

Grade 3 = severe AE

Grade 4 = life-threatening AE or urgent intervention indicated

Grade 5 = death

Events grade 1 or higher will be recorded on the appropriate AE eCRF for this study.

For grading an abnormal value or result of a clinical or laboratory evaluation (including, but not limited to, a radiograph, an ultrasound, an electrocardiogram etc.), a treatment-emergent AE is defined as an increase in grade from baseline or from the last post-baseline value that doesn't meet grading criteria. Changes in grade from screening to pre-treatment and enrollment at Day 0 will also be recorded as AEs, but are not treatmentemergent. If a specific event or result from a given clinical or laboratory evaluation is not included in the NCICCTCAE manual, then an abnormal result would be considered an AE if changes in therapy or monitoring are implemented as a result of the event/result.

For additional information and a printable version of the NCI-CTCAE manual, consult the NCI-CTCAE web site: <http://ctep.cancer.gov/reporting/ctc.html>.

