12.8.2.1 Planned DSMB Reviews

The DSMB shall review safety data at least yearly during planned DSMB Data Review Meetings. Data for the planned safety reviews will include, at a minimum, a listing of all reported AEs and SAEs.

12.8.2.2 *Ad hoc* DSMB Reviews

In addition to the pre-scheduled data reviews and planned safety monitoring, the DSMB may be called upon for *ad hoc* reviews when an event occurs that is of sufficient concern to the DAIT/NIAID Medical Monitor and/or the protocol chair(s) to warrant DSMB review, this includes all Expedited Safety Reports. The DSMB will be notified within 24 to 48 hours by the NIAID Medical Monitor and will promptly review any event that potentially impacts safety at the request of the protocol chair or DAIT/NIAID or any occurrence that meets the definition of the *Study Stopping Rules* defined in [Section 11.5](#).

After review of the data, the DSMB will make recommendations regarding study conduct and/or continuation.

12.8.2.2.1 Temporary Suspension of Enrollment and Study Treatment for *ad hoc* DSMB Safety Review

A temporary halt in screening, enrollment, and investigational product application will be implemented if an *ad hoc* DSMB safety review is required. New participants will not be consented for study participation during the enrollment and treatment halt. Participants who were screened or who completed the Pre-treatment Visit but who are not yet randomized will not be allowed to continue with the Day 0 Treatment Visit. All participants not randomized within 14 days of the Screening Visit must rescreen. Follow up visits will continue per the Schedule of Events.

13. Statistical Considerations and Analytical Plan

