1. PROTOCOL SYNOPSIS (VERSION 3.0)

Title	A Pilot Study to Evaluate the Survival of Transplanted Staphylococcus Hominis A9 on the Skin of Adults with Moderate-to-Severe Atopic Dermatitis
Short Title	Targeted Investigation of Microbiome Elimination (TIME-1)
Clinical Phase	Phase 1
Number of Sites	1 Clinical Site in the United States
IND Sponsor/Number	NIAID / IND # 17286

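### Stopping rule 2 names Grade 3 only, so a related Grade 4 adverse event that neither the investigator nor the sponsor judges serious triggers no mandatory pause

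*Protocol*

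**What the plan says.** Protocol section 11.5 gives two reasons for which screening, enrollment and treatment application stop pending DSMB review. Rule 1 is any SAE with a reasonable possibility of having been caused by the product. Rule 2 is "The development of any severe (Grade 3) AE for which attribution is defined as related or possibly related". The Study Stopping Rules row of the Protocol synopsis words rule 2 identically. So does the same row in SAP section 1, which reproduces the synopsis of protocol version 3.0.

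Grades are defined in Protocol section 12.3.1. Severe is the label for Grade 3 alone. The next category is "Grade 4 = life-threatening AE or urgent intervention indicated", and Grade 5 is death.

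Seriousness is a separate classification in section 12.2.3. It depends on outcome, "in the view of either the investigator or the Sponsor". Life-threatening events and death are on the list. Other important medical events may be classed as serious on medical judgment; one example given is "allergic bronchospasm requiring intensive treatment in an emergency room or at home".

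**The concern.** Read literally, rule 2 applies to one grade and sets no minimum. The protocol does write out a minimum when it means one: section 12.3.1 states that "Events grade 1 or higher will be recorded on the appropriate AE eCRF for this study". Rule 2 has no such wording in any of the three places where it appears.

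The result is an inversion. A related, non-serious Grade 3 event forces a suspension. A related Grade 4 event that nobody classes as serious does not, although it is worse. A stopping rule is there to take the decision to pause out of individual hands when a signal appears. In this one cell the decision goes back to individuals, in a Phase 1 trial of a live bacterial product in a new vehicle. Each participant has a single application, so those at stake are participants treated after the event.

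**Working it through.** No figure in the plan depends on this point, so the main check compares the wording of the relevant sections.

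**1. Every grade and seriousness combination, for a related or possibly related AE.** The rules are from section 11.5, the grades from 12.3.1 and seriousness from 12.2.3.

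| Event | Rule 1 (related SAE) | Rule 2 (Grade 3) | Mandatory pause? |
|---|---|---|---|
| Grade 3, not serious | no | yes | yes |
| Grade 3, serious | yes | yes | yes |
| Grade 4, serious (includes every life-threatening event) | yes | no | yes |
| Grade 4, not judged serious by investigator or sponsor | no | no | **no** |
| Grade 5 (death, serious by definition) | yes | no | yes |

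The fourth row is the only related event of Grade 3 or above that meets neither rule. It can arise because Grade 4 has two alternatives. The life-threatening one is a listed seriousness outcome. The urgent-intervention one is not listed, and it becomes serious only through the important-medical-event clause, which is permissive.

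**2. Other routes to a pause for that row.**

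- Ad hoc DSMB review (section 12.8.2.2) can be called for an event "of sufficient concern to the DAIT/NIAID Medical Monitor and/or the protocol chair(s) to warrant DSMB review", or at the request of the protocol chair or DAIT/NIAID. If such a review is required, section 12.8.2.2.1 applies: "A temporary halt in screening, enrollment, and investigational product application will be implemented". No SAE classification is needed, but someone has to decide to ask.
- The same section covers any occurrence that meets section 11.5, so it inherits the rule 2 wording.
- It also covers expedited safety reports. Under section 12.5.2.2 these need a serious, unexpected suspected reaction or a broader finding of significant human risk.
- Reporting speed differs. SAEs go to the sponsor within 24 hours (section 12.5.1). The scheduled route for a non-serious AE to the Medical Monitor is a monthly report (section 12.8.1).

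**3. Illustrative exposure.**

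Inputs: at least 20 participants, one application each, and about 18 months for recruitment, enrollment and follow-up (Protocol synopsis). Because the 18 months include follow-up, I also use a 12-month treatment window, which is my assumption. The lag to the next monthly report is between 0 and 1 month. Its mean is 0.5 month if the event time is uniform within the month, also an assumption.

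- Application rate: 20 / 18 = 1.11 per month; 20 / 12 = 1.67 per month.
- Mean further applications before the report: 0.5 × 1.11 = 0.56; 0.5 × 1.67 = 0.83.
- At the longest lag: 1 × 1.11 = 1.11; 1 × 1.67 = 1.67.

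Earlier notice makes these numbers smaller. They count applications up to the point where the Medical Monitor is informed; a pause after that would still be discretionary.

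**The case against.** The strongest case against is that the cell is almost empty and the intention is obvious.

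- The important-medical-event language in section 12.2.3 overlaps heavily with an event needing urgent intervention, and one party's view is enough to make it serious. The gap therefore needs a product-related event, urgent enough for Grade 4, that both the investigator and the sponsor call non-serious.
- A common source of non-serious Grade 4 events, the asymptomatic laboratory value, is largely absent. No blood draw is scheduled, and blood is taken only at unscheduled visits at the investigator's discretion (section 5.4.5).
- No DSMB or Medical Monitor is likely to pause for Grade 3 and carry on after Grade 4.
- SAP section 10.1 calls for DSMB review of an event that could contribute to a predefined stopping rule, which is looser than meeting the rule exactly.
- The exposure estimate reflects the monthly reporting cycle, which applies equally to a non-serious Grade 3 event and which the proposed edit leaves unchanged.

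Much of this stands. The event is unlikely, Grade 3 was probably meant as a minimum, and the exposure figure gives a scale for the consequence; it does not measure the effect of the missing words. What does not stand is that the other provisions close the gap. The important-medical-event clause is permissive, the ad hoc review is either discretionary or refers back to section 11.5, and SAP section 10.1 depends on the same predefined rules. None of them makes the pause mandatory.

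**Conclusion.** The point holds as a minor wording error in a safety threshold. As written, a related Grade 4 AE judged non-serious by both the investigator and the sponsor meets neither stopping rule, while a milder related Grade 3 AE stops the trial. Life-threatening events and deaths are covered by rule 1, and participants in the remaining cell still have the discretionary ad hoc review.

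The likelihood is low and the exposure small: on the assumptions above, roughly one further application if the event waits for a monthly report. The conclusion about the wording does not depend on that figure.

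One limit applies. The full protocol available is version 2.0, while the SAP reproduces the version 3.0 synopsis. Rule 2 is unchanged in that synopsis, but the body of version 3.0, including its sections 11.5, 12.2, 12.3 and 12.8, could not be checked.

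**What to change.** Reword rule 2 to start from *any severe or worse (Grade 3 or higher) AE* and keep the attribution condition as it is. Make the change in Protocol section 11.5, in the Protocol synopsis, and in the synopsis reproduced in SAP section 1. Section 12.8.2.2 needs no edit because it refers to section 11.5. The cost is a few words in three places at the next amendment, with no effect on data, sample size or analysis.
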